Recombinant human chorionic gonadotropin (r-hCG)(Ovidrel® Prefilled Syringe, Serono) will be purchased from Serono, Inc., Rockland, MA or Switzerland. Participants will receive a subcutaneous injection of 250 microgram-recombinant hCG three times a week (Monday, Wednesday and Friday) for 12 weeks. The first dose of study drug will be administered by a registered nurse. At that time, she will instruct each participant in the self-administration of the study drug in a skin fold of the upper abdominal region. Participants will return to receive doses 2 and 3, where they will be observed by the registered nurse in the self-administration of the drug for mastering of the skill and to answer any additional questions. The remainder of the drug doses will be self-administered by the participants or a partner trained in the procedure in their homes. All participants will be seen by a study physician once a month during the treatment phase for a history and physical exam and blood collection.

Protocol tissue collection

Normal breast tissue specimens will be collected by CNB at the beginning of treatment (0 day), at the end of treatment (90 days) and at six months post-treatment (270 days - 36 weeks). CNB specimens will be primarily utilized for analysis of genomic expression by cDNA microarray, RNA sequencing and epigenomic studies. In addition, a series of surrogate intermediate markers such as cytomorphologic evaluation and cell proliferation index will be analyzed. The primary objective is to compare the gene expression, and epigenomic profiles of sampled breast epithelial cells across the three time points (Fig. 1), before and after treatment, and identify differentially expressed or silenced genes (as determined by ≥ 2 fold change). Gene expression measurements will be obtained at baseline (time 0), after treatment with hCG at 90 days (time 1), and at 270 days from baseline (time 2). We are interested in comparing the expression profiles between all pairs of time points as well as across time. The comparison of profiles before and after treatment with either hCG, both at 90 and 270 days, are of particular interest (Figure 1).

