Asymptomatic women of all racial and ethnic groups who are carriers of a deleterious mutation in the BRCA1 gene, as determined by testing in a CLIA-certified clinical genetics laboratory; ECOG performance status 0 (Karnofski 100%); no clinical evidence of breast cancer; premenopausal women between the ages of 20-40; must have normal menstrual cycles and intact ovaries; nulliparous or parous women are eligible; not on oral contraceptives or hormone replacement therapy, and if taking them, stopped six weeks prior to the initiation of treatment and the performance of the Core Needle Biopsy (CNB) and blood drawing; currently not participating in a chemoprevention trial for breast cancer or currently taking tamoxifen for chemoprevention; no history of prior cancer other than non-melanoma skin cancer; normal ovarian size report from pelvic ultrasound; ability to understand and willing to sign a written informed consent document; willing to self-administer or have the hCG administered 3 X per week by a partner, over three months and to return for two repeat CNB. Subjects may not be pregnant because the effects of human chorionic gonadotropin on the developing human fetus are unknown. Subjects will be required to have a negative urine or serum pregnancy test within 72 hours of the 1st dose. Human chorionic gonadotropin is highly elevated in the serum of pregnant women, and is therefore not expected to be teratogenic. Nevertheless, women of child-bearing potential must agree to use adequate contraception, including barrier method of birth control, abstinence or tubal ligation performed prior to study entry and for the duration of study participation. Should a woman become pregnant or suspect she is pregnant while participating in this study, she should inform her treating physician immediately.

Exclusion criteria

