Participants receiving any other agents, investigational or otherwise for the purpose of primary prevention; history of allergic reactions attributed to compounds of similar chemical or biologic composition to hCG preparations or one of its excipients; receiving medications that could interfere with the study protocol objectives such as hormonal contraceptives, androgens, prednisone, thyroid hormones, or insulin; previous treatment with follicle stimulating hormone for assisted reproduction; uncontrolled intercurrent illness including, but not limited to ovarian enlargement of undetermined origin, ongoing or active infection, NYHA ≥ class 1 congestive heart failure, unstable angina pectoris, cardiac arrhythmia, severe cognitive deficit or

psychiatric illness/social situations that could make her unable to give informed consent or would limit compliance with study requirements; HIV-positive, or infection with hepatitis B or C.

Criteria for Removal from Study:

Participants will be removed from study if they manifest any grade 2 or greater adverse reaction attributable to the recombinant hCG, non-compliance with treatment, or if the participant becomes pregnant. The reason for study removal and the date the participant was removed must be documented in the case report form. Subjects removed for reasons other than toxicity may be replaced.

Study assessment and procedures

A study physician will obtain written informed consent from the participants according to institutional and Federal guidelines. A questionnaire and a baseline physical exam will be performed along with a complete blood count, serum chemistries and a baseline beta hCG (which will also serve as a pregnancy test, when applicable). Baseline and repeat CNBs will be performed by the study surgeon.

Hematology and chemistries will be repeated monthly during the 90-day treatment period and 30 days after the final injection.

In the absence of treatment delays due to adverse events, treatment will continue for 12 weeks or until one of the following criteria applies: intercurrent illness that prevents further administration of treatment; unacceptable adverse event(s); participant decides to withdraw from the study, or; general or specific changes in the participant's condition render the participant unacceptable for further treatment in the judgment of the investigator.

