All the tubes containing CNB samples collected as described need to be kept at 4°C before shipping. As an additional measure each sample tube should be wrapped with Parafilm to prevent possible leakage during shipment. The samples have to be shipped by overnight express mail to the Breast Cancer Research Laboratory at the Fox Chase Cancer Center with frozen ice packs in the Styrofoam box. The samples need to be packed tightly so they do not move during shipping. The shipments should be sent Monday through Thursday to ensure the samples are collected accordingly and not to ship on *Fridays to ensure that the samples do not sit for an extended period of time.*

Special Studies

The following special correlative studies will be performed:

- #1, Histopathological evaluation of epithelial cell normality;
- #2, evaluation of cell proliferation by Ki67 immunohistochemistry;
- #3, serum analysis for hormone level and biomarker determinations;
- # 4, genomic analysis of breast epithelial cells from CNB.

Genomic DNA and total RNA will be extracted using ALLPrep DNA/RNA Mini Kit (QIAGEN) according to manufacture instructions.

Special Correlative study #1 - Cell Morphology and Proliferation:

Histopathological analysis - Outcome measures: A minimum of two slides will be made one for histology and another one for Ki-67.

Special Correlative study #2 - Cell proliferation - Ki67 index:

Total epithelial cells will be delineated with Mayer's hematoxylin counter stain and proliferating cells with a MIB-1 (DAKO M7240) antibody for Ki-67.

Special Correlative study #3 - Serum analysis for hormone level and biomarker determination:

At the time of each CNB, whole blood will be collected by venipuncture and stored in the FCCC Breast Cancer Research Laboratory at -80°C for batch determination of hormonal levels and aliquots will be stored for future studies. All serum assays for estradiol, progesterone and human chorionic gonadotropin will be conducted at the Breast Cancer Research Laboratory of the FCCC.

Special Correlative study #4 - Gene expression analysis.

Affymetrix U133plus2.0 microarrays will be used in this follow-up gene expression study involving 25 women each in the hCG treatment arm. Gene expression measurements will be obtained at baseline (before treatment) and at 3 months and 9 months after the respective treatment. We will identify genes that are

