significantly up or down regulated at 3 months following treatment. In addition, we will compare the post- and pre-treatment differences and identify genes showing significantly altered expression. We will repeat the above analyses using the post-treatment expression at 9 months.

Analysis of biomarker data.

In addition to microarray data, we will obtain expression levels of Ki67, ER, PR, estradiol, progesterone and hCG using serum assays at baseline (before treatment) and at 3 months and 9 months after treatment. We will identify markers that are significantly up or down regulated at 3 months following treatment. In addition, we will compare the post- and pre-treatment differences and identify markers showing significantly altered expression. We will repeat the above analyses using the post-treatment expression at 9 months.

Statistical Considerations.

The primary efficacy analyses for the phase I/II study will concern baseline to 3-month follow-up changes in gene expression profiles measured by microarray methods as follows. For each woman i at biopsy time point j (0 =pre-treatment, 1 =3 month follow-up) we will compute the Mahalanobis distance between RMA normalized expression microarray data derived from the biopsy and the prototypic gene profile. We will denote this distance as $D(i,j)$. If $D(i,1) < D(i,0)$ we will declare woman i a “success”. This would indicate the post-treatment profile (genomic signature) is closer than the pre-treatment profile to the prototypic gene profile. At the conclusion of the study we will sum the number of successes for each arm. Whichever arm has a higher proportion of successes is declared the “preventive choice”. With complete pre-treatment and post-treatment expression microarray data on 25 women we will correctly identify the changes in terms of “success” with at least 85% probability. Assuming a drop-out rate of 20%, we would need to enroll a total of 25 participants per arm.

In secondary analyses we will use an exact one-sided, one-sample test ($\alpha=0.05$) to assess the null hypothesis of no drug induced change in $D(i,j)$ (i.e., a null hypothesis that the probability of “success” is 0.5.). With data from 18 women we will have at least 80% power to detect the alternative hypothesis that the true probability of “success” is 0.80. We will also characterize the change in distance (i.e., $\Delta D(i)=D(i,1)-D(i,0)$) using standard methods (e.g., mean, median, standard deviations, etc.).

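### Biopsies and hormone samples in naturally cycling women are timed by calendar day only, so menstrual phase adds uncontrolled variation to the before/after contrasts, most clearly at 9 months

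*Protocol*

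**What the plan says.** The inclusion criteria (Participant selection) ask for "premenopausal women between the ages of 20-40; must have normal menstrual cycles and intact ovaries". Oral contraceptive and hormone users are eligible only after a washout: "not on oral contraceptives or hormone replacement therapy, and if taking them, stopped six weeks prior to the initiation of treatment", and the same six weeks apply to the biopsy and blood draw. The exclusion criteria rule out women "receiving medications that could interfere with the study protocol objectives such as hormonal contraceptives, androgens, prednisone, thyroid hormones, or insulin".

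Protocol tissue collection fixes the sampling days: "Normal breast tissue specimens will be collected by CNB at the beginning of treatment (0 day), at the end of treatment (90 days"), and a third biopsy "at six months post-treatment (270 days - 36 weeks"). The flow chart in the Dutch summary gives weeks 1, 12 and 36.

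Special Correlative study #3 ties the blood sample to the biopsy: "At the time of each CNB, whole blood will be collected by venipuncture", with estradiol, progesterone and hCG assayed. Under Analysis of biomarker data, "we will compare the post- and pre-treatment differences and identify markers showing significantly altered expression", first at 3 months and then at 9 months.

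Statistical Considerations counts a woman as a success if her expression profile lies closer to the prototypic profile at 3 months than at baseline. A secondary exact one-sided test sets this against a success probability of 0.5. The LIMMA analysis also works on changes from before to after treatment and is repeated at 9 months.

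**The concern.** The eligibility rules select women whose own estradiol and progesterone rise and fall each month and remove the drugs that would suppress this. The washout shows that the protocol regards hormone exposure as able to affect the biopsy and blood results. The endogenous cycle gets no such care: apart from the washout and a pregnancy test within 72 hours of the first dose, nothing visible governs where in the cycle a sample falls.

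All planned contrasts compare a woman with herself over time. Statistical Considerations mentions arms and a control group, but only hCG treatment is described, so no concurrent group shows what the cycle alone would do. Three things are at stake:

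- precision of the success count and of the gene-level and Ki67 changes;
- the 9-month contrast, which is off drug and so fully open to natural phase differences;
- attribution of serum estradiol and progesterone changes to the drug, because these are the hormones that define the cycle.

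**Working it through.** **1. Do the calendar days preserve phase?** For an exact 28-day cycle (assumed):

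| Sampling day | Remainder | Shift from baseline phase |
|---|---|---|
| 84 (12 weeks × 7) | 84 − 3×28 = 0 | none |
| 90 | 90 − 3×28 = 6 | 6 days later |
| 252 (36 weeks × 7) | 252 − 9×28 = 0 | none |
| 270 | 270 − 9×28 = 18 | 18 days later, or 10 earlier |

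The protocol equates 270 days with 36 weeks, which differ by 18 days, and 90 days of treatment with 12 weeks, which differ by 6. Real cycles also vary. A simulation assumed a uniform start day, a 14-day luteal phase, a mean cycle of 28 days, and SDs of 2 to 3 days both between and within women. If cycles continued naturally, follicular/luteal phase would differ from baseline in about 45–46% of women at day 90 and about 50% at day 252 or 270. Once cycles vary this much, calendar timing gives almost no phase matching at 9 months.

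**2. The protocol's own power figure.** Inputs from Statistical Considerations: 18 women, one-sided α = 0.05, null success probability 0.5, alternative 0.80, power at least 80%.

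- P(X ≥ 13 | 18, 0.5) = (8568 + 3060 + 816 + 153 + 18 + 1)/262144 = 12616/262144 = 0.048.
- P(X ≥ 12 | 18, 0.5) = (12616 + 18564)/262144 = 0.119, so 13 is the smallest allowable cut-off.
- Power = P(X ≥ 13 | 18, 0.80) = 0.867. The stated figure is reproduced.

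**3. What added cycle variation would do.** Treat the change in distance as normal, so that success probability 0.80 corresponds to a standardised shift of 0.8416. If the cycle adds a fraction f to the variance of the change, p = Φ(0.8416/√(1+f)). The protocol gives no value for f, so a range is shown:

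| f (assumed) | 0.8416/√(1+f) | p | Power, n = 18 |
|---|---|---|---|
| 0 | 0.842 | 0.800 | 0.867 |
| 0.25 | 0.753 | 0.774 | 0.796 |
| 0.5 | 0.687 | 0.754 | 0.731 |
| 1 | 0.595 | 0.724 | 0.625 |

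**4. Noise or bias?** With no drug effect, if a woman's pair of phases is as likely to occur in one order as in the other, the change in distance is symmetric about zero. The success probability then stays at 0.5, and the loss is of power only. Bias needs a systematic phase difference between visits, for example baselines clustered in one part of the cycle and follow-ups in another.

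**The case against.** **A reader might infer that the test's false-positive rate is inflated.** Had phase alone moved the null success probability to 0.60 or 0.65, the rate at n = 18 would be 0.21 or 0.36 instead of 0.048. The protocol does not support that step. It does not say that treatment starts after menses, the 72-hour pregnancy test implies no cycle day, and 0.60 and 0.65 have no source. Only the weaker statement stands: the plan could neither prevent nor detect such a shift.

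**A reader might also infer that estradiol and progesterone changes cannot be interpreted at all.** That goes too far. Group mean changes can still be estimated if phase is not systematically different between visits, and the hormone levels themselves carry some phase information at baseline and at 9 months. What is weak is a single woman's change, and attribution to the drug without an untreated comparison.

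**The power illustration can be challenged.** The planned 0.80 may already include all within-woman variation, in which case deducting cycle variance counts it twice. The model treats a Mahalanobis distance as if cycle variance simply added to the variance of its change. The test is labelled secondary. At f = 0.25 power is still close to the stated 80%. These points stand, so the figures are illustrative only.

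**Forcing all baselines into one cycle window could do harm.** With day 90 left on the calendar and under repeated hCG, it could create the systematic misalignment it was meant to avoid. Day-90 hormones may also be drug effects, so adjusting for them, or selecting women by day-90 phase, could remove part of the treatment effect. This stands and limits the remedy.

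**Visibility.** Figure 1, the CRF and the baseline questionnaire are not shown, and a history is taken monthly, so cycle day may be captured somewhere. How phase enters the models can be left to an analysis plan. But no analysis plan can recover a date that was not collected or re-time a biopsy already taken.

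**Conclusion.** The point holds as a design weakness of moderate weight. Naturally cycling women are sampled by calendar day, and no visible section records or matches phase, so the cycle adds uncontrolled within-woman variation to the before/after contrasts. It is clearest for the 9-month contrast and for attributing estradiol and progesterone changes to the drug.

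Its size is not known. At 18 women, power would fall from 0.87 to between about 0.80 and 0.63 if the cycle adds 25% to 100% to the variance of the change. This rests on the assumptions that 0.80 excludes cycle noise and that expression and Ki67 respond to the cycle, neither of which the protocol quantifies. Bias is possible but not shown. At day 90, where repeated hCG may itself alter the cycle, drug and phase cannot be fully separated by any scheduling rule.

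**What to change.** In Protocol tissue collection:

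- Record the date of the last menstrual period at every biopsy and blood draw.
- Schedule the 9-month biopsy and blood draw in the same cycle phase as that woman's own baseline, within a stated window around the nominal day. The 270-day and 36-week statements must be reconciled before that day can be named.

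In the analysis:

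- For the baseline-to-9-month contrast only, use cycle day, supported by the estradiol and progesterone already assayed, as a covariate or in a phase-matched sensitivity analysis.
- For the baseline-to-3-month contrast, do not adjust for on-treatment estradiol or progesterone and do not select women by day-90 phase. Report results by baseline phase, and state that drug and phase cannot be fully separated there.

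Cost: one CRF field and a 9-month visit window of about two weeks either side. No extra visit, biopsy or assay is needed.

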In exploratory analyses we will use LIMMA to identify genes whose expression changes significantly from pre- to post-treatment. Statistical significance will be measured by p-values adjusted for FDR using the method of Benjamini and Hochberg (108). Genes showing an FDR of less than 5% will be considered statistically significant. Biological significance will be measured by fold change. Genes showing more than 2-fold change in either direction (up and down regulated) will be considered biologically significant. Differentially expressed genes from each of the above filters will be combined and a list of common genes showing greater statistical and biological significance (lower q-values and up/down regulated by more than 2-fold) will be identified. Finally, we will use various bioinformatics methods (pathway analyses, enrichment analyses, etc.) to extract additional biological insights into the drug-induced changes in normal breast tissue. All of the above analyses will be repeated to examine baseline to 9-month follow-up differences. Assuming approximately 20000 genes of relevance in the study, a total sample size of 36 women/arrays (i.e., 18 each) will enable us to detect effect sizes of 1.39, 1.32 and 1.27 if the number of truly differentially expressed genes is 500, 1000 and 1500 respectively, with a power of 80% and a false discovery rate (FDR) of 5%. These calculations are based on the approach outlined in (105). In terms of \log_2 expression, an effect size of 1.32 corresponds to a 2.5-fold difference in gene expression between the control group and each treatment.

Mining for pathways and exploratory analyses:

In this study we are proposing two major high throughout genomic data platforms such as microarray and next generation sequencing platforms. The data mining and bioinformatics pipelines for both platforms are different. Following is a description of these data analyses pipelines.

Microarray data Mining:

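### The protocol names two different primary targets and two gene-calling rules, and neither primary criterion, as labelled, has error control

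*Protocol*

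**What the plan says.** Three statements bear on this.

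- **Protocol tissue collection.** "The primary objective is to compare the gene expression, and epigenomic profiles of sampled breast epithelial cells across the three time points", and to "identify differentially expressed or silenced genes (as determined by ≥ 2 fold change". The scope is wide: "We are interested in comparing the expression profiles between all pairs of time points as well as across time". The section covers microarray, RNA sequencing and epigenomic work. No p-value, alpha or FDR appears there.
- **Statistical Considerations, primary and secondary analyses.** "The primary efficacy analyses for the phase I/II study will concern baseline to 3-month follow-up changes in gene expression profiles measured by microarray methods". The endpoint is per woman: "If $D(i,1) < D(i,0)$ we will declare woman i a “success", where D is the Mahalanobis distance to a prototypic profile. The decision rule is to prefer the arm with the higher proportion of successes. The exact one-sided test at 0.05 against a success probability of 0.5 is placed under secondary analyses.
- **Statistical Considerations, exploratory analyses.** "In exploratory analyses we will use LIMMA to identify genes whose expression changes significantly from pre- to post-treatment". Here "Genes showing an FDR of less than 5% will be considered statistically significant", using Benjamini-Hochberg. More than 2-fold change is a second filter, and the final list holds the genes that pass both. The analyses are then repeated for baseline to 9 months.

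**The concern.** The two statements called primary differ in endpoint, time points and platforms. The task called primary in one section is exploratory in another, under a different calling rule. Nothing in the protocol reconciles them.

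This is not detail that can be left to an analysis plan. The protocol itself fixes both versions, so a plan that follows one departs from the other. The results can also diverge: a long list of 2-fold genes may accompany a null distance count, or the reverse, and either could be reported as addressing the primary aim. The section on expected results intends the signature to become an intermediate biomarker for larger prevention trials, so it matters which result carries the claim and what error rate stands behind it.

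**Working it through.** **1. The statements side by side**

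| | Protocol tissue collection | Statistical Considerations, primary | Statistical Considerations, exploratory |
|---|---|---|---|
| Label | primary objective | primary efficacy analysis | exploratory |
| Target | gene and epigenomic changes | women whose distance falls | gene changes |
| Times | all pairs of three | baseline to 3 months | baseline to 3 months, repeated at 9 |
| Rule | at least 2-fold | arm with higher proportion | FDR below 5% and more than 2-fold |
| Error control | none stated | none (exact test is secondary) | FDR 5% |

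The middle column compares arms, but the study treats one group. The right-hand column does not cover the 90-to-270-day pair, nor the epigenomic calls in the objective.

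**2. The protocol's own figures**

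*Exact test.* Inputs from the secondary analyses: n = 18, p0 = 0.5, p1 = 0.80, one-sided alpha 0.05. The smallest admissible cut-off is 13 successes:
- P(X ≥ 13 | 18, 0.5) = 0.048 (a cut-off of 12 gives 0.119)
- P(X ≥ 13 | 18, 0.80) = 0.867

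The stated power of at least 80% is reproduced. With 20 completers (25 × 0.80, from the stated 20% drop-out), the cut-off is 15: alpha 0.021, power 80.4% (a cut-off of 14 gives alpha 0.058).

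*FDR sizing.* Inputs: 20,000 genes, 18 arrays per group, power 80%, FDR 5%, m1 true genes. Per-gene alpha* = m1 × 0.8 × 0.05 / ((20,000 − m1) × 0.95). Detectable effect = (z(1 − alpha*/2) + z(0.8)) × √(2/18).

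| m1 | alpha* | computed effect | stated effect |
|---|---|---|---|
| 500 | 0.00108 | 1.37 | 1.39 |
| 1000 | 0.00222 | 1.30 | 1.32 |
| 1500 | 0.00341 | 1.26 | 1.27 |

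The two-group normal formula comes close to the stated values, so the effect sizes are in units of the per-array SD.

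**3. The planning SD**

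The protocol equates an effect size of 1.32 with a 2.5-fold difference. Since log2(2.5) = 1.32, the per-array SD is about 1 log2 unit. The SD of a within-woman change is then √(2(1 − r)), where r is the within-woman correlation. The protocol does not give r. At r = 0.5 the paired SD is 1.0; at r = 0 it is 1.41.

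**4. What a 2-fold rule alone would pass**

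Two-fold means a mean log2 change of at least 1 in absolute value. For a gene with no true change, the chance of passing is 2 × (1 − Φ(√n / SD)). Assumptions: normal errors, one SD for all genes, 20,000 null genes.

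| Pairs | Paired SD | √n / SD | Chance per gene | Expected false genes |
|---|---|---|---|---|
| 20 | 1.0 | 4.47 | 0.0000077 | 0.15 |
| 20 | 1.41 | 3.17 | 0.0015 | 30 |
| 18 | 1.0 | 4.24 | 0.000022 | 0.44 |
| 18 | 1.41 | 3.01 | 0.0026 | 52 |

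These are counts per comparison, and the objective asks for three pairs of time points. With 20 pairs the count changes about 200-fold (30 / 0.15) between two plausible correlations.

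**The case against.** Much of the case for leaving the text alone is fair.

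- **No rival success criterion.** A reader might infer that the trial could be declared positive on whichever criterion turns out well. The documents do not support that. The gene objective has no success threshold: no required number of genes and no decision attached. The only decision rule is the one on the distance. What stands is a descriptive objective labelled primary that matches neither the primary analysis nor the gene-calling rule.
- **Gene calls do have error control.** A reader might infer from the objective that they have none. The exploratory paragraph supplies FDR control. The fault is that this control sits under a different label and a different rule from the objective.
- **The size is modest.** A reader might infer hundreds of false genes. That needs a paired SD near 2.0, which gives about 507 with 20 pairs. With a per-array SD of 1 it requires 4 = 2(1 − r), so r = −1, which does not fit the protocol's own planning. In the protocol's scenario of 500 true genes with effect 1.39, at r = 0 and 20 pairs, fold change alone gives about 31 false and 446 true calls, a false discovery rate of about 6%. With 18 pairs it is about 11%. Noisier genes would do worse.
- **The study is exploratory.** Study design calls it that, and the Specific aim is proof of principle. This lowers the stakes, but Statistical Considerations still names primary efficacy analyses, so the mismatch remains.

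**Conclusion.** The inconsistency is real and rests on the text alone: two statements of what is primary, two gene-calling rules, and no reconciliation. As labelled, neither primary criterion carries error control. One uses fold change only; the other uses a comparison of arms in a single-group study, with its test demoted to secondary.

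The numerical consequence of the fold-change rule is limited but not fixed: about 0.15 to 30 false genes of 20,000 per comparison. That range rests on 20 pairs, the implied per-array SD of 1 log2 unit, an assumed within-woman correlation from 0.5 to 0, normal errors and one common SD. The sponsor should fix this; it does not undermine the design.

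**What to change.** 1. Name one primary endpoint and one time point, and state them identically under Protocol tissue collection and Statistical Considerations. The choice is the sponsor's.
2. If it is the 3-month proportion of women whose distance falls, as Statistical Considerations already has it, make the existing one-sided exact test against 0.5 its primary test in place of the comparison of arms. Both sizes in step 2 of the working keep at least 80% power at a true success probability of 0.80. Without this step the primary analysis would remain untested.
3. Keep the 270-day and epigenomic comparisons, labelled secondary or exploratory.
4. Replace the fold-change-only definition in the objective with the rule already written in the exploratory paragraph (FDR below 5% and more than 2-fold), and apply it wherever genes are called, including comparisons that the paragraph does not now cover.

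The cost is protocol wording. No visit, biopsy or sample size changes. The downside is a shorter gene list.
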